2 ANALYSIS POPULATIONS

The following populations for analyses are defined:

Table 3 - Populations for analyses

Period	Population	Description
Primary analysis	Screened	All participants (and/or participant's parent(s)/legal guardian(s)) who signed the Informed Consent Form (ICF).
	Randomized	All participants from screened population who have been allocated to a randomized intervention by Interactive Response Technology (IRT) regardless of whether the intervention was received or not.
	Population without trial impact (disruption) due to COVID-19	All randomized participants without any critical or major deviation related to COVID-19 and who didn't permanently discontinue treatment due to COVID-19 and who didn't permanently discontinue study due to COVID-19.
	Primary efficacy population	All randomized participants with diagnosis of late-onset GM2 gangliosidosis aged ≥ 18 years. Participants will be analyzed according to the intervention assigned by randomization.
	Primary PD population	All randomized participants with diagnosis of late-onset GM2 gangliosidosis aged ≥ 18 years who received at least 1 dose of study medication and who have baseline and postbaseline assessments of PD. Participants will be analyzed according to the intervention they actually received.
	Primary PK population	All randomized participants with diagnosis of late-onset GM2 gangliosidosis aged ≥ 18 years who received at least 1 dose of study medication and who have at least 1 PK assessment.
	Primary safety population	All randomized participants with diagnosis of late-onset GM2 gangliosidosis aged ≥ 18 years who received at least 1 dose of study medication. Participants will be analyzed according to the intervention they actually received.
	Secondary efficacy population	All enrolled participants with a clinical diagnosis of juvenile/adolescent late-onset GM2 gangliosidosis, GM1 gangliosidosis, Saposin C deficiency, Sialidosis Type 1, or juvenile/adult galactosialidosis.
	Secondary PD population	All enrolled participants with a clinical diagnosis of juvenile/adolescent late-onset GM2 gangliosidosis, GM1 gangliosidosis, Saposin C deficiency, Sialidosis Type 1, or juvenile/adult galactosialidosis, who received at least 1 dose of study medication and who have baseline and postbaseline assessments of PD.

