	Secondary PK population	All enrolled participants with a clinical diagnosis of juvenile/adolescent late-onset GM2 gangliosidosis, GM1 gangliosidosis, Saposin C deficiency, Sialidosis Type 1, or juvenile/adult galactosialidosis, who received at least 1 dose of study medication and who have at least one PK assessment.
	Secondary safety population	All enrolled participants with a clinical diagnosis of juvenile/adolescent late-onset GM2 gangliosidosis, GM1 gangliosidosis, Saposin C deficiency, Sialidosis Type 1, or juvenile/adult galactosialidosis, who received at least 1 dose of study medication.
Open-Label extension	Enrolled population	All participants who completed the primary treatment analysis period and accept to continue.
	Efficacy population	All participants from enrolled population.
	Safety population	All participants from enrolled population who received at least one venglustat dose after the 104-week visit.

Participants exposed to study intervention before or without being randomized will not be considered randomized and will not be included in any analysis population. The safety experience of these participants will be reported separately.

Randomized participants for whom it is unclear whether they took the study intervention will be considered as exposed and will be included in the safety population as randomized.

For any participant randomized more than once, only the data associated with the first randomization will be used in any analysis population. The safety experience associated with any later randomization will be reported separately.

For participants receiving more than one study intervention during the study, the intervention group for as-treated analyses will be the one to which the participant was treated with the longest duration.

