3.6 SAFETY ANALYSES

All safety analyses will be performed on the safety populations as defined in [Section 2](#) for the two steps analysis, unless otherwise specified, using the following common rules:

- The analysis of the safety variables will be essentially descriptive, and no testing is planned.
- Safety data in participants who do not belong to the safety population (eg, exposed but not randomized) will be provided separately if any.

In the first step analysis, safety data will be presented for the following period:

- Safety analysis of the primary analysis period. This analysis will present safety data collected during the primary analysis period (as defined in [Section 3.1](#)). Safety analyses will present safety data in the following arms:
 - Primary population – Placebo: participants from the primary population, having received placebo during the primary analysis period.
 - Primary population – Venglustat: participants from the primary population, having received venglustat during the primary analysis period.
 - Secondary population – Venglustat: participants from the secondary population, having received venglustat during the primary analysis period.

In the second step analysis, safety data will be presented separately for the two following periods:

- Safety analysis of the OLE period. This analysis will present safety data collected during the OLE period (as defined in [Section 3.1](#)). Only participants having received venglustat during the OLE period will be included in this analysis. Safety analyses will present safety data from the following groups:
 - Primary population - Delayed venglustat: participants from the primary population, having received placebo during the primary analysis period, then having received venglustat during the OLE period.
 - Primary population - Early venglustat: participants from the primary population, having received venglustat during the primary analysis period, then having continued to receive venglustat during the OLE period.

- Primary population - All venglustat: all participants from the primary population having received venglustat during the OLE period.
- Secondary population – Venglustat: participants from the secondary population having received venglustat during the OLE period.

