3.7.2 Pharmacodynamic analyses

In the first step analysis for the secondary population, the pharmacodynamic endpoint correspond to the primary endpoint and is described in [Section 3.2.4](#).

In the first step analysis for the primary population, the CSF GM2 parameter correspond to the primary and secondary endpoint. It is described in [Section 3.2.1](#) and [Section 3.3.1.2.1](#).

In the second step analysis for the secondary population, plasma samples for GL-1 and other biomarkers according to the disease (see [Section 1.2](#)) will be summarized on the PD population.

Plasma samples for GL-1, GM2 and CSF sample for GL-1 will be summarized on the pharmacodynamics primary population.

The CSF sample is only available in the primary analysis period. So, the measurement in CSF will be presented only in first step analysis.

Exploratory endpoints include percent change in:

- GL-1 from baseline to Week 104 (primary population in CSF and Plasma sample).
- GM2 from baseline to Week 104 (primary population in Plasma sample).
- GL-1 from baseline to Week 208 (primary and secondary population in Plasma sample).
- GM2 from baseline to Week 208 (primary population and secondary if applicable in Plasma sample).
- GM1 or GM3 from baseline to Week 208 (secondary population when applicable in Plasma sample).

Additional plasma and CSF biomarkers that may include lipidomics, glycoprotein nonmetastatic protein B (gpNMB) and neurofilament will be summarized on the PD primary and secondary populations if any.

Each PD variable will be summarized using descriptive statistics at each time point, including assessment of observed values, change and percent change from baseline.

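### The longest-duration rule for as-treated groups is not limited to a period, so read literally it labels former-placebo participants by visit timing in the Week 208 plasma GL-1 and GM2 summaries

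*SAP*

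**What the plan says.** The notes after Table 3 in SAP Section 2 contain the rule. Its opening words set the scope: "For participants receiving more than one study intervention during the study, the intervention group for as-treated analyses will be the one". The criterion that completes the sentence is the intervention "to which the participant was treated with the longest duration". Nothing confines it to one analysis period, and equal durations are not addressed.

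In the same table, the primary PD population consists of treated participants "who have baseline and postbaseline assessments of PD. Participants will be analyzed according to the intervention they actually received". The row sits in the primary-analysis block. The OLE block lists enrolled, efficacy and safety populations but no PD population.

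SAP 3.6 groups safety data differently, by period. The first-step placebo arm is "participants from the primary population, having received placebo during the primary analysis period". The delayed venglustat group in the OLE is "participants from the primary population, having received placebo during the primary analysis period, then having received venglustat during the OLE period".

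SAP 3.7.2 plans exploratory PD endpoints beyond Week 104, among them percent change in "GL-1 from baseline to Week 208 (primary and secondary population in Plasma sample", and the same for plasma GM2. It places the plasma GL-1 and GM2 summaries on the primary PD population and gives no early or delayed grouping. SAP 3.1 makes presentation by intervention group the default unless something else is specified.

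**The concern.** A longest-duration rule normally handles dispensing errors: a participant who took the wrong kit for a while is counted under what they mostly took. As worded, this one also captures the planned switch. SAP 3.1 defines the primary analysis period, the OLE period and the end of the study as separate things, so a rule whose scope is the whole study takes in the OLE.

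Every placebo participant who continues therefore meets the condition, and the two planned durations are the same. The deciding quantity is then the difference between two visit dates, which carries no pharmacological information. In the Week 208 plasma summaries, the venglustat column would mix people treated for about four years with people treated for about two. The placebo column would consist of people then taking venglustat or who had recently stopped it.

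**Working it through.** The plan gives no figure for how many participants the rule would relabel, so there is none to reproduce.

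**Inputs**
- Planned durations: 104 weeks of placebo, then 104 weeks of venglustat (SAP 1.1).
- Target days: Week 104 = D728 and Week 208 = D1456 (SAP Table 13).
- Visit windows: ±7 days at Week 104, ±14 days at Week 208 (protocol 1.3). The first OLE dose is taken the day after the Week 104 visit.
- Placebo n = 19, venglustat n = 38 (SAP Section 4). The SAP 5.6.3.3 code uses 10% dropout by two years.
- Assumptions: whole-day visits, uniform and centred in each window; last dose of each period on the visit day. The documents state neither.

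**Step 1: durations.** Let A be the Week 104 deviation (−7 to 7) and B the Week 208 deviation (−14 to 14).
- Placebo days = 728 + A.
- Venglustat days = (1456 + B) − (728 + A) = 728 + B − A.
- Venglustat is longer when B > 2A.

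**Step 2: count.** There are 15 × 29 = 435 combinations.
- Ties (B = 2A): one for each A, so 15/435 = 3.4%.
- The other 420 split evenly by symmetry: 210/435 = 48.3% venglustat longer and 48.3% placebo longer.
- If the Week 208 clock starts at OLE entry, the condition becomes B > A and the counts are the same.
- Moving a last-dose day by one day changes the venglustat share to between 45% and 52%.

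**Step 3: people.**
- No dropout: 19 × 0.483 = 9.2, about 9 of 19.
- 10% dropout in each period (the second is assumed): 19 × 0.9 × 0.9 = 15.4 completers, and 15.4 × 0.483 = 7.4, about 7 of 15. As a share of the 17.1 OLE entrants this is 7.4/17.1 = 43%, because those who stop early in the OLE keep the placebo label.

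**Step 4: visits not centred.** Protocol Appendix 11 allows a three-month extension in an emergency, with blinded treatment continued until a delayed Week 104 visit.
- A quarter of Week 104 visits 15 to 90 days late, Week 208 still counted from Day 1: none of these can have venglustat longer (B would have to exceed 30), so the share is 0.75 × 0.483 = 36%. If all are late it is 0%.
- A quarter of Week 208 visits 15 to 90 days late: all of these have venglustat longer, so the share is 0.75 × 0.483 + 0.25 = 61%.

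**Step 5: which outputs are exposed.**

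| Output | Exposed? | Reason |
|---|---|---|
| First step, including co-primary CSF GM2 and Week 104 plasma PD | No | SAP 3.8.2 excludes OLE data |
| 9-HPT and other efficacy in the primary efficacy population | No | Analysed as randomized (Table 3) |
| Safety, both steps | No | SAP 3.6 names groups by period |
| PK | No | First step only (SAP 3.7.1) |
| Second-step plasma GL-1 and GM2, primary population | Yes | As-treated population, no other visible grouping rule |

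**The case against.** The strongest reply is that context already limits the rule. As-treated wording appears in two rows of Table 3, primary PD and primary safety, both in the primary-analysis block. SAP 3.2.1.3.1 describes as-treated as a departure from the randomized allocation, not as the planned switch. On that reading the sponsor meant dispensing errors only, and no programmer would relabel a delayed-start participant. That is probably the intent, but the sentence does not say so: it follows the whole table, including the OLE rows, and its scope is the study. Part of the exploratory text is also blacked out, so a grouping rule may exist there that cannot be seen.

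Four stronger readings are tempting, and the documents do not support them:
- *The co-primary or safety results are at risk.* They are not; see Step 5.
- *Sections 2 and 3.6 contradict each other on safety.* The wordings differ, but 3.6 is the specific section and 3.1 lets a specific rule override the default.
- *The venglustat effect is diluted by about 20%.* With 38 true and 9.2 relabelled participants, 9.2/47.2 = 19%, if placebo shows no change. This could arise only if second-step tables re-display visits up to Week 104 under this label. At Week 208 the relabelled participants have had about 104 weeks of venglustat, so the figure does not apply.
- *An early-versus-delayed comparison would be lost.* SAP 3.7.2 plans descriptive PD summaries and no such comparison.

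**Conclusion.** Wrong as written, minor severity. Followed literally, the Section 2 rule sorts placebo participants who complete the OLE by visit timing. About 48% would be labelled venglustat, 48% placebo and 3% left without a rule, or roughly 7 of 15 to 9 of 19 people called venglustat. This rests on visits being uniform and centred in the windows; in the late-visit cases checked the share runs from about 36% to 61%, and to 0% if every Week 104 visit is late. The size is uncertain, but in each case scheduling decides the label. The reach is one family of outputs, the second-step plasma GL-1 and GM2 summaries in the primary population, which are descriptive and exploratory. No confirmatory, safety, PK or Week 104 first-step result depends on it.

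**What to change.** Three short edits to the SAP:
1. In Section 2, state that the longest-duration rule applies only to interventions received within the primary analysis period, and that planned venglustat in the OLE does not change a participant's group.
2. Add a tie rule, for example the randomized group.
3. In Section 3.7.2, present Week 208 PD in the primary population by the early and delayed venglustat groups already defined in Section 3.6.

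The cost is a few sentences. Trial conduct, data collection and the confirmatory analyses do not change. It is best done before unblinding, so that the grouping is fixed without knowledge of the data.

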2.1.1 Estimands

Primary estimand defined for main endpoints are summarized in below [Table 4](#). More details are provided in [Section 3](#).

Table 4 - Summary of primary estimand for main endpoints

Endpoint Category (estimand)	Estimands			
	Endpoint	Population	Intercurrent event(s) handling strategy	Population-level summary (Analysis and missing data handling)
Primary population				
Primary objective: To assess the efficacy of daily oral dosing of venglustat when administered over a 104-week period.				
Primary endpoint (treatment policy)	Annualized rate of change in the 9-HPT from baseline to Week 104	Primary efficacy population	Regardless of adherence to study intervention	Difference in mean slope of the 9-HPT from baseline to Week 104, estimated from a linear mixed effect model after log transformation. In case of outliers, the linear mixed effect model will be replaced by a robust ANCOVA on individual slopes. No imputation of missing data due to small sample size.
Primary objective: To assess the PD of daily oral dosing of venglustat when administered over a 104-week period.				
Primary endpoint (treatment policy)	Percent change in CSF GM2 biomarker from baseline to Week 104	Primary pharmacodynamic population	Regardless of adherence to study intervention	Difference in mean percent change in CSF GM2 biomarker from baseline to Week 104, estimated from ANCOVA. In case of outliers, the ANCOVA will be replaced by a robust ANCOVA. No imputation of missing data due to small sample size.
Secondary objectives: To assess the PD of daily oral dosing of venglustat when administered over a 104-week period				
Secondary endpoint (treatment policy)	Absolute change in CSF GM2 biomarker from baseline to Week 104	Primary pharmacodynamic population	Regardless of adherence to study intervention	Difference in mean absolute change in CSF GM2 biomarker from baseline to Week 104, estimated from ANCOVA. In case of outliers, the ANCOVA will be replaced by a robust ANCOVA. No imputation of missing data due to small sample size.
Secondary objectives: To assess the effect of venglustat on selected performance test and scale over a 104-week period.				
Secondary endpoint (treatment policy)	Change in 25FWT from baseline to Week 104	Primary efficacy population (participants able to walk at baseline)	Regardless of adherence to study intervention	Difference in mean slope of change in the 25FWT from baseline to Week 104, estimated from a linear mixed effect model after log transformation. In case of outliers, the linear mixed effect model will be replaced by a robust ANCOVA on individual slopes. No imputation of missing data due to small sample size.

Endpoint Category (estimand)	Estimands			
	Endpoint	Population	Intercurrent event(s) handling strategy	Population-level summary (Analysis and missing data handling)
Secondary endpoint (treatment policy)	Change in FARS-neuro from baseline to Week 104	Primary efficacy population	Regardless of adherence to study intervention	Difference in mean slope of estimated FARS-neuro from baseline to Week 104 using a linear mixed effect model. In case of outliers, the linear mixed effect model will be replaced by a robust ANCOVA on individual slopes. No imputation of missing data due to small sample size.
Secondary population				
Primary objective: To assess PD response (plasma and CSF GL-1 biomarker and disease specific biomarkers) of venglustat when administered once daily over a 104-week period.				
Primary endpoint (treatment policy)	Plasma and CSF GL-1 biomarker and a pathway specific biomarker will be assessed as described in Section 3.2.4 .	Secondary PD population	Regardless of adherence to study intervention	Descriptive
Secondary objectives: To assess the effect of venglustat on selected performance tests and scale over a 104-week period				
Secondary endpoint (treatment policy)	Annualized rate of change in the 9-HPT from baseline to Week 104	Secondary efficacy population	Regardless of adherence to study intervention	Descriptive
Secondary endpoint (treatment policy)	Change in 25FWT from baseline to Week 104	Secondary efficacy population	Regardless of adherence to study intervention	Descriptive
Secondary endpoint (treatment policy)	Change in FARS-neuro from baseline to Week 104	Secondary efficacy population	regardless of adherence to study intervention	Descriptive

3 STATISTICAL ANALYSES

3.1 GENERAL CONSIDERATIONS

Statistical significance for comparison between venglustat and placebo will be assessed at the Type I error rate of 0.05 one sided. Although a typical criterion for concluding that a trial is positive is a p-value of <0.05 two-sided, a higher Type I error rate of 0.05 one-sided was selected due to the rarity of late-onset GM2 gangliosidosis, the seriousness of this disease and lack of available therapy, as per Food and Drug Administration (FDA) draft guidance (1).

In general, continuous data will be summarized using the number of observations available, mean, standard deviation (SD), median, [Q1, Q3] minimum, and maximum. Categorical and ordinal data will be summarized using the count and percentage of participants.

The baseline value is defined as the last available value before or equal to the first dose of investigational medicinal product (IMP) date in the primary analysis period. For participants randomized but not exposed, the baseline value is defined as the last available value before or equal to the date of randomization.

Unless otherwise specified, analyses will be performed by intervention group (and overall for baseline and demographics characteristics).

The two analysis periods described below are defined:

- The **primary analysis period** is defined as the period starting at the date of signed informed consent, and ending at the end of Week 104 visit, or the day before the first IMP OLE administration (whichever comes last). For participants not exposed to IMP in the OLE, the primary analysis period ends at the date of end of study.
- The **OLE period** (only for participants exposed to IMP in the OLE) is defined as the period starting the day after the end of primary analysis period, until the end of the study.

Within each analysis period, the following observation periods are defined:

During the **primary analysis period** (as defined above), the following observation periods are defined:

- The **pre-treatment period** is defined as the time from the signed informed consent date up to the first IMP administration.
- The **treatment-emergent (TE) period** is defined as the time from the first IMP administration to the last administration of IMP during the primary analysis period +6 weeks (including any temporary treatment discontinuation period, if any) or the end of the primary analysis period (whichever comes first).

The TE period includes the following 2 periods:

- **The on-treatment period** is defined as the time from the first administration of IMP to the last administration of IMP in the primary analysis period +1 day (including any temporary treatment discontinuation period, if any).
- **The residual treatment period**, if any is defined as the time from the end of the on-treatment period to the end of the TE period.
- **The post-treatment period** is defined as the period starting the day after the end of the TE period, up to the end of the primary analysis period.

During the **OLE period** (as defined above), the following observation periods are defined:

- **The treatment-emergent (TE) period** is defined as the time from the start of the OLE period to the last administration of the OLE IMP +6 weeks (including any temporary treatment discontinuation period, if any).

The TE period includes the following 2 periods:

- **The on-treatment period** is defined as the time from the start of the OLE period to the last administration of the OLE IMP +1 day (including any temporary treatment discontinuation period, if any).
- **The residual treatment period** is defined as the time from the end of the on-treatment period to the end of the TE period.
- **The post-treatment period** is defined as the period starting the day after the end of the TE period up to the end of the study.

In addition, the overall venglustat treatment-emergent period will combine the primary analysis period and the OLE period:

- The **overall venglustat treatment-emergent period** is defined as the time from the first intake of venglustat to the last intake of venglustat +6 weeks (including any temporary treatment discontinuation period, if any). Depending on the treatment received during the primary analysis period (venglustat or placebo), the first intake of venglustat may be either during the primary analysis period or during the OLE period.

The on-study observation period is defined as the time from the first administration of the IMP until the end of the study (defined as the last scheduled visit for those who completed the study and the end-of-study date collected on electronic case report form (e-CRF) page “Completion of End of Study” for those who did not complete the study. If death is the end-of-study reason, date of death will be used.

